September 26, 2021

**Evaluation of Plasma Cholecystinin (CCK) Levels and Gallbladder (GB) Functions in
Hyperemesis Gravidarum**

NCT 03950167.

Background: The pathophysiology of hyperemesis gravidarum (HG) remains poorly understood. A multifactorial origin, including infective, anatomical and psychological factors, and hormonal changes of pregnancy has been proposed. Altered cholecystinin (CCK) levels may have potential consequences on gastric emptying, which may be related to nausea and vomiting. In this context, alterations in CCK secretion in women diagnosed with HG have been previously reported, and alterations in CCK levels lead to impaired gallbladder (GB) functions.

Objective: In this study, we aimed to evaluate fasting and post-prandial CCK levels, and GB function in HG patients.

Design: Prospective cohort study

Methods: HG patients who present before the end of the 14th week of gestation at our obstetrics outpatient clinic, with persistent vomiting and routine prenatal visits, will be recruited. The required evaluations, including the collection of venous blood samples and sonographic evaluation of GB functions, will be performed at the initial assessment.

After a 12-hour overnight fasting period, venous blood samples will be collected for routine haematological, biochemical, hormonal tests and CCK levels. Transabdominal ultrasonography (US) will be performed to assess GB functions. Subsequently, a fatty test meal (100 g of milk chocolate) will be administered to the patients. The postprandial CCK concentrations at 15 min after meal intake will be measured. The postprandial GB volume (PGv) will be measured using the same US equipment by the same radiologist for each patient at the 45th minute after the meal

Statistical analysis:

Statistical analyses will be performed using SPSS for Windows, version 22.0 (SPSS Inc., Chicago, IL, United States). Since this is the first study comparing both CCK levels and GB functions in patients diagnosed with HG and healthy pregnant women, a power analysis is not feasible. The distribution of continuous variables (normal or skewed) will be determined with the Shapiro-Wilks test. Levene's test will be used for the evaluation of the homogeneity of variances. Unless specified otherwise, continuous data will be described as mean \pm SD for normal distributions, and median (inter-quartile range) for skewed distributions. The two groups will be compared with Student's t-test for normally distributed variables and the Mann-Whitney U test for the data that were not normally distributed. Degrees of relation between the variables will be evaluated with the Pearson or Spearman correlation analysis. A p value of <0.05 will be accepted as significant in all statistical analyses.

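### Anti-vomiting drug use before the visit is neither recorded nor analysed, so a drug effect on CCK or gallbladder volume, if there is one, could not be told apart from an effect of HG

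*Combined protocol and SAP*

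**What the plan says.** All references are to the combined protocol and SAP.

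- **Cases (Methods).** HG patients presenting before the end of week 14 "at our obstetrics outpatient clinic, with persistent vomiting and routine prenatal visits, will be recruited".
- **Timing (Methods).** Blood sampling and "sonographic evaluation of GB functions, will be performed at the initial assessment". The plan does not say that women are untreated at that point.
- **Standardisation before the test (Methods).** "After a 12-hour overnight fasting period, venous blood samples will be collected for routine haematological, biochemical, hormonal tests and CCK levels". Fasting is the only preparation described.
- **Comparator (Statistical analysis).** The controls appear only in the remark that this is the first study "comparing both CCK levels and GB functions in patients diagnosed with HG and healthy pregnant women". No eligibility or medication criteria are given for them.
- **Analysis (Statistical analysis).** "The two groups will be compared with Student's t-test for normally distributed variables and the Mann-Whitney U test" for skewed data, and "Degrees of relation between the variables will be evaluated with the Pearson or Spearman correlation analysis". The correlated variables are not named. There is no covariate, stratification or sensitivity analysis.

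Medication is not mentioned anywhere in the document: no exclusion, no record of use, no time of last dose.

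**The concern.** The symptom that brings a woman into the HG group is also the reason she might already be taking something for it. A woman recruited as a healthy control has less reason to. Drug use is then tied to group membership by the recruitment rule itself, which is confounding by indication. If any such drug alters CCK release or gallbladder volume, the two-group test attributes the alteration to HG.

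The error can run either way. A drug effect could create a difference where HG has none, or cancel part of a real one. A larger sample does not help, because it makes a biased estimate more precise. The information is also hard to recover later: if drugs and time of last dose are not written down on the test day, neither the investigators nor a reader can establish whether exposure was absent or common.

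**Working it through.** **Check of the text.** Every section was read for a restriction, record, washout or adjustment concerning medication. There is none. The plan states no sample size or effect size, so it has no figure of its own to reproduce.

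**Inputs.** From the plan: significance at p < 0.05 and an unadjusted two-group test. The plan does not state sidedness; two-sided is assumed. Everything else is also assumed:
- share of HG women exposed, f = 0.3, 0.5, 0.7; no controls exposed
- shift in the endpoint caused by the drug, d = 0.2 or 0.5 SD
- n = 40 or 60 per group
- no true effect of HG

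**Formula.** The spurious difference between group means is f × d, in SD units. The two-sample t statistic then has noncentrality λ = f × d × √(n/2) on 2n − 2 degrees of freedom. The false-positive rate is the probability that it falls beyond ±t(0.975, 2n − 2), which is 1.991 for n = 40 and 1.980 for n = 60.

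Example: f = 0.5, d = 0.5, n = 40. The shift is 0.25 SD, λ = 0.25 × √20 = 1.118, and the rejection probability is 19.7%.

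| d (SD) | f | f × d (SD) | 40 per group | 60 per group |
|---|---|---|---|---|
| 0.2 | 0.3 | 0.06 | 5.8% | 6.2% |
| 0.2 | 0.5 | 0.10 | 7.3% | 8.4% |
| 0.2 | 0.7 | 0.14 | 9.5% | 11.8% |
| 0.5 | 0.3 | 0.15 | 10.2% | 12.9% |
| 0.5 | 0.5 | 0.25 | 19.7% | 27.4% |
| 0.5 | 0.7 | 0.35 | 34.0% | 47.7% |

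With f = 0.1 and d = 0.5 at 40 per group the rate is 5.6%, and with f = 0 it is 5%. The inflation therefore runs from negligible to serious, depending on inputs the plan does not supply.

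**Bias in the other direction.** If HG truly shifts an endpoint by 0.5 SD and a drug taken by half the HG women shifts it back by 0.5 SD, the visible difference is 0.5 − 0.5 × 0.5 = 0.25 SD. At 40 per group, power falls from about 60% to about 20%.

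**Can the two be separated once use is recorded?** Yes, provided some HG women are unexposed. In a linear model with a group term and a drug-use term and no exposed control, the fitted group coefficient equals mean(unexposed HG) − mean(controls). A simulated data set confirmed this to machine precision. Adjustment and restriction to unexposed women thus give the same point estimate in that case. Both fail if every HG woman is exposed.

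**How much can the restricted comparison bear?** At f = 0.7 and 40 per group, 12 unexposed HG women face 40 controls. The standard error is √(1/12 + 1/40) = 0.33 SD and the 95% half-width about 1.96 × 0.33 = 0.65 SD. A true difference of 0.3 SD would take the wrong sign with probability Φ(−0.3/0.33) ≈ 18%. That is too imprecise to decide the study's conclusion.

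**The case against.** The strongest reply is that this is conjecture. Persistent vomiting describes a symptom, not prior treatment. Testing takes place at the initial assessment, which limits exposure to anything started because of that visit. The document does not say that any woman took a drug, and does not say that such a drug alters either endpoint.

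Much of this stands, and it rules out several stronger readings that a reader might infer:

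- **That controls take no such drugs.** The document says only that they are healthy. The argument needs unequal use, not zero use among controls; the zero in the table is an assumption.
- **That the Background establishes the mechanism.** It says "Altered cholecystinin (CCK) levels may have potential consequences on gastric emptying, which may be related to nausea and vomiting", and that altered CCK impairs gallbladder function. The direction is from CCK to emptying. A drug that changes emptying and thereby CCK or gallbladder volume is a different path, and the document does not describe it.
- **That a drug effect will be reported as an HG effect.** Neither exposure nor a drug effect is shown, so the document supports only that it could be.
- **That adjustment cannot help because exposure lies almost wholly in the HG group.** The identity above shows that it can, as long as some HG women are unexposed.

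The core survives the reply. Testing at the first visit does not exclude earlier use, and without a record nobody can show that exposure was rare.

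**Conclusion.** The omission is confirmed. It is an inexpensive improvement to make, not a demonstrated flaw in the result. As written, the plan cannot distinguish an effect of prior drug use on CCK or gallbladder volume from an effect of HG. The table's false-positive rates, from about 6% to about 48%, show what could follow. They rest on assumed exposure, an assumed drug effect, an assumed sample size and no exposed controls. At the low end the problem hardly matters, and only a record of use would tell the investigators which end they are at.

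**What to change.** 1. On the test day, record for every woman in both groups each anti-vomiting, motility or acid-suppressing drug and the time of the last dose.
2. Report use by group.
3. Prespecify a supportive sensitivity analysis of each CCK and gallbladder endpoint that compares unexposed HG women with unexposed controls. When no control is exposed, a model with group and drug-use terms is equivalent. Fix the look-back period that defines unexposed before the data are seen, and report an estimate with its confidence interval.
4. State that this analysis informs interpretation and does not veto the main comparison. A rule requiring the subset to agree would be unsound, given the imprecision shown above.

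The cost is one case-report field and one extra table. The downside is that the unexposed HG women are fewer and possibly milder cases, so the interval is wider and a difference that grows with severity may look smaller there. No treatment is withheld or changed.

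### The plan describes no masking of the gallbladder ultrasound reader or the CCK laboratory to HG status, which leaves the group comparison open to reading bias

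*Combined protocol and SAP*

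**What the plan says.** The Methods section gives one line on the fasting scan: "Transabdominal ultrasonography (US) will be performed to assess GB functions". After the chocolate test meal, the gallbladder volume "will be measured using the same US equipment by the same radiologist for each patient at the 45th minute after the meal". For the hormone it says "The postprandial CCK concentrations at 15 min after meal intake will be measured", in addition to the fasting sample.

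The Statistical analysis section describes the study as "comparing both CCK levels and GB functions in patients diagnosed with HG and healthy pregnant women". It plans that "The two groups will be compared with Student's t-test for normally distributed variables and the Mann-Whitney U test" (the latter for non-normal data), and that "A p value of <0.05 will be accepted as significant in all statistical analyses". No sample size is given, on the ground that "a power analysis is not feasible".

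Neither section mentions masking, blinding, coded images, coded tubes, stored images or repeat reading. The plan also does not say how volume is computed, whether gallbladder function will be expressed as an ejection fraction, or how the CCK assay runs are organised.

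**The concern.** Gallbladder volume from ultrasound depends on the person who chooses the plane and places the measurement points. Fixing the equipment and the reader limits variation between devices and readers. It does nothing about what the reader knows. HG patients are recruited with persistent vomiting, so their group is likely to be apparent to whoever scans them. A reader who also took the fasting measurement may know that value when measuring at 45 minutes. The Background links altered CCK to impaired gallbladder function, so a reader could hold an expectation about direction even though the Objective is neutrally worded.

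If readings shift even slightly with group, the shift enters the comparison as if it were biology. It does not shrink with more women; a larger sample only makes it more likely to reach significance. The analysis contains nothing that could separate it from a real difference. The same reasoning applies to the CCK assay if samples are identifiable by group or run in separate batches, although no size can be put on that from the documents.

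**Working it through.** There is no stated figure to reproduce: the plan gives no sample size, power, effect size, standard deviation or measurement error. The calculation below shows only how a small reading bias carries through to the test.

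**From the document:** two groups, unadjusted t-test (or Mann-Whitney), significance at 0.05.

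**Assumed:** two-sided test; volume proportional to the product of three diameters; the same systematic difference c in each diameter between groups; no true group difference; between-woman coefficient of variation (CV) of volume 40%, varied from 30% to 50%; n = 30 or 50 per group.

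**Step 1, bias in volume:** b = (1 + c)³ − 1.
- c = 1%: 1.01³ − 1 = 3.0%
- c = 3%: 1.03³ − 1 = 9.3%
- c = 5%: 1.05³ − 1 = 15.8%

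**Step 2, bias in standard errors:** λ = b / (CV × √(2/n)). For c = 3%, CV 40%, n = 50: 0.0927 / (0.40 × 0.20) = 1.16.

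**Step 3, false-positive rate:** the probability that a noncentral t variable with 2n − 2 degrees of freedom and noncentrality λ falls outside the two-sided 5% limits. At CV 40%:

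| Bias per diameter | Bias in volume | Bias in SDs | n = 30 per group | n = 50 per group |
|---|---|---|---|---|
| 1% | 3.0% | 0.08 | 6.0% | 6.6% |
| 3% | 9.3% | 0.23 | 14.3% | 20.9% |
| 5% | 15.8% | 0.39 | 32.3% | 49.6% |

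A normal approximation agrees to within about one percentage point (for example 14.6% and 21.3% in the 3% row).

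**Sensitivity:** for c = 3% and n = 30, a CV of 30% gives 21.8% and a CV of 50% gives 10.9%. Over a wider grid (c from 1% to 5%, CV 30% to 50%, n from 20 to 100 per group, normal approximation), the rate runs from 5.4% to 96.0%.

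**Ejection fraction:** let EF = 1 − (postprandial volume / fasting volume).
- If both scans carry the same proportional bias it cancels. With a 10% bias in each volume and a true EF of 60%, 1 − (0.4 × 1.1)/(1 × 1.1) = 60%.
- If only the postprandial reading is biased by 3% per diameter, observed EF = 1 − 0.4 × 1.0927 = 56.3%, a loss of 3.7 points. With an assumed SD of 15 points, false positives are 15.6% at 30 per group and 23.2% at 50.

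**The case against.** The strongest objection is that the point rests on silence and on assumed inputs. Much of this is right, and it limits what can be claimed.

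- **The reader is not shown to be unmasked.** A reader of the plan might infer that volumes are measured live by someone who knows the group. The text does not say so. It gives a time for the measurement but does not say when the measurement points are placed on the image, and it is silent about knowledge of group. What stands is that no masking is described.
- **A single radiologist for the whole study is not stated.** The phrase can mean only that one woman's two scans share a reader. This does not weaken the point: if readers differ between women, reader differences could also line up with group.
- **The bias size is not an estimate for this study.** No document gives a 3% or 5% shift, a CV, a group size or a volume formula. At 1% per diameter and CV 40% the inflation is small. The figures show that modest bias could matter, not that it will.
- **Direction and endpoint are open.** The Objective is neutral, no directional hypothesis is stated and no primary ultrasound measure is named.
- **An ejection fraction would remove a bias common to both scans.** This is correct, but the plan names the postprandial volume as a measurement and never defines an ejection fraction. A bias confined to the second reading would survive.

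The objection does not remove the gap. An operator-dependent outcome is compared between groups that are likely to be visibly different, with no described safeguard against knowledge of group.

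**Conclusion.** The point holds as a gap in the measurement procedure that should be closed, not as a demonstrated distortion. Under the stated assumptions at CV 40%, a reading bias of 1%, 3% or 5% per diameter gives roughly 6-7%, 14-21% or 32-50% false positives on volume with 30 to 50 women per group, against a nominal 5%. These rates depend wholly on assumed values for bias, variability, group size and volume formula.

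A reader might go further and conclude that coded images and tubes would prevent a false group difference. That is not supported. Coding the images masks the measurement but not the capture: whoever holds the probe still sees the woman and chooses which view to save. Coding the tubes protects the CCK assay and has no bearing on gallbladder readings. If masking removed all group-related bias, the error rate would return to 5% per test, but nothing in the documents allows the removable share to be calculated.

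**What to change.** State in the Methods whether the ultrasound reader and the CCK laboratory are masked to HG status, and add the following:

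1. Store the fasting and 45-minute images under a study code. Have the same radiologist measure them afterwards, in an order that mixes the groups, without group labels.
2. Use the same radiologist and the same device for both groups, and say so.
3. Label the CCK tubes with the study code only, and mix HG and control samples within each assay run.

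The cost is image storage and some later reading time by the same radiologist. No extra reader, scan or blood draw is needed. Image capture remains unmasked, and the report should name this as a remaining limitation.

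### Does the plan need a sample size and a precision statement, given that its reason for having no power analysis is weak?

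*Combined protocol and SAP*

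**What the plan says.** The Statistical analysis section has one sentence on study size. It reads "Since this is the first study comparing both CCK levels and GB functions in patients diagnosed with HG and healthy pregnant women" and concludes that "a power analysis is not feasible". No number of HG women, number of healthy pregnant women or ratio between them follows.

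The Objective is descriptive: "we aimed to evaluate fasting and post-prandial CCK levels, and GB function in HG patients". It does not rank the outcomes. Methods describes recruitment only for "HG patients who present before the end of the 14th week of gestation at our obstetrics outpatient clinic"; the healthy comparators appear only in the Statistical analysis section.

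The comparison itself is specified: "The two groups will be compared with Student's t-test for normally distributed variables and the Mann-Whitney U test", the latter for data that are not normal. The threshold is also given: "A p value of <0.05 will be accepted as significant in all statistical analyses". Planned summaries are mean and SD, or "median (inter-quartile range) for skewed distributions". No confidence interval for a group difference is mentioned.

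The Background adds that "alterations in CCK secretion in women diagnosed with HG have been previously reported", without figures.

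**The concern.** The stated reason does not lead to its conclusion. A power or precision calculation does not need an earlier study of both outcomes together. It needs one outcome and either a standardised difference or a target interval width. The Background also acknowledges earlier CCK findings in HG, so the field is not wholly without precedent.

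What follows from having no size is the practical worry. A p value of 0.05 or more from a small study may mean that there is no difference, or only that too few women were studied. With no planned size, named primary outcome, difference of interest or interval, the plan gives a reader little to tell these apart. The gap is widest for outcomes summarised by median and inter-quartile range, where a reader cannot rebuild an interval from mean, SD and n.

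**Working it through.** **Inputs from the documents.** Significance level 0.05 (taken as two-sided, since sidedness is not stated); two independent groups; t-test or Mann-Whitney. The documents give no group size, SD, effect size or power target, so there is no figure of the plan's own to reproduce.

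**Assumptions.** Normal data, equal variances, groups of 20 to 100 in a 1:1 ratio, true differences of 0.5 or 0.8 SD. These illustrate; they are not trial figures.

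**Step 1: is a calculation possible?** Yes. The 95% interval half-width, in SD units, is t(0.975, 2n−2) × √(2/n). For n = 30 this is 2.002 × √(2/30) = 2.002 × 0.258 = 0.517. Power comes from the noncentral t distribution with noncentrality d × √(n/2).

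| n per group | Half-width (SD) | Difference detectable at 80% power (SD) | Chance of p ≥ 0.05, true 0.5 SD | Chance of p ≥ 0.05, true 0.8 SD |
|---|---|---|---|---|
| 20 | 0.640 | 0.909 | 66% | 31% |
| 30 | 0.517 | 0.736 | 52% | 14% |
| 40 | 0.445 | 0.634 | 40% | 6% |
| 50 | 0.397 | 0.566 | 30% | 2% |
| 100 | 0.279 | 0.398 | 6% | 0% |

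The ratio matters too. With 30 HG women and 15, 30 or 60 controls, the detectable difference is 0.906, 0.736 or 0.633 SD. For 80% power at 0.5 SD, 64 per group are needed.

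**Step 2: does this show that the study is underpowered?** No. The chance of missing 0.5 SD runs from 66% to 6% over the sizes tried, and nothing in the documents places the study on that range. The figures also describe the t-test on normal data. They do not cover the skewed outcomes, for which the interval gap is largest.

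**Step 3: does the Background contradict the Statistical analysis section?** No. One says that CCK alterations were reported; the other says that nobody has compared CCK and GB function jointly. Both can be true. Whether the earlier reports give usable means and SDs cannot be told from the documents.

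**Step 4: what would a stricter reading rule achieve?** Suppose a margin of 0.5 SD were fixed in advance, and 'no material difference' were written only when p ≥ 0.05 and the whole 95% interval lies within ±0.5 SD. Simulation with 400,000 replicates gives:

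| n per group | 'No material difference', true difference 0 | Same reading, true difference 0.5 SD (an error) |
|---|---|---|
| 20 | 0.2% | 0.1% |
| 30 | 3.9% | 0.6% |
| 40 | 19.9% | 1.8% |
| 50 | 39.4% | 2.4% |
| 100 | 88.1% | 2.5% |

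The rule protects well against a false reassurance. At 30 per group with no true difference, however, about 5% of studies are significant by chance and 4% read 'no material difference', which leaves 100 − 5 − 4 = 91% inconclusive.

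**A point of scale.** The half-width first falls below 0.5 SD at 32 per group (0.4997; 31 gives 0.508). That is in units of the observed SD. On the true-SD scale used in the simulation the boundary is not sharp, which is why 3.9% of studies with 30 per group still fall within the margin.

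**The case for a change.** The strongest case for a change is that the repair is cheap: one corrected sentence, stated numbers, a primary outcome or an exploratory label, and one interval per comparison. The omissions are real, since no redaction or missing table falls where these items would stand. Without a closing rule or a primary outcome, nothing fixes in advance when recruitment ends or which comparison carries the conclusion. The plan never calls itself exploratory, so that defence is not available from its own words.

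Much of this stands. The sentence on power is poorly reasoned, and the omissions leave a null result harder to read. What does not stand is the step from there to a needed change. Stating the achieved numbers and adding intervals (a Hodges-Lehmann shift beside Mann-Whitney) completes the report without altering a planned test. Sizing the groups from a chosen difference amounts to asking for more women, with no difference in the documents on which to base the request. A margin rule adds an equivalence-style test to an observational study that claims no equivalence. Reporting intervals and drawing no conclusion of no difference from p ≥ 0.05 alone gives nearly the same protection.

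**Conclusion.** No change to the plan follows. The reason given for omitting a power analysis is insufficient, but correcting it would alter neither a test nor the data collected. The planned comparisons keep their validity whatever the group sizes. The possible harm, reading a non-significant result as no difference, depends on an interpretation that the plan does not make and that ordinary reporting of group sizes and intervals guards against.

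The size of the problem is undetermined: a 6% to 66% chance of missing a 0.5 SD difference, on assumed 1:1 groups of 100 down to 20, normal data and a two-sided 5% level. The documents do not show where the study lies within that range. The one substantive addition considered, a preset margin, is a trade-off on which statisticians could reasonably differ, given its 91% inconclusive rate at 30 per group under a true difference of zero.

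### Levene's test is scheduled but leads to nothing and Student's t-test is the only mean comparison named; the plan should commit in advance to Welch's t-test

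*Combined protocol and SAP*

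**What the plan says.** The whole rule is in the Statistical analysis section of the combined protocol and SAP.

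- **Normality check:** "The distribution of continuous variables (normal or skewed) will be determined with the Shapiro-Wilks test".
- **Variance check:** Levene's "test will be used for the evaluation of the homogeneity of variances". No later sentence uses the result.
- **Two-group test:** Student's "t-test for normally distributed variables and the Mann-Whitney U test for the data that were not normally distributed". Normality is the only stated criterion, and no unequal-variance version of the t-test is named.
- **Level:** "A p value of <0.05 will be accepted as significant in all statistical analyses". Sidedness is not stated.
- **Size:** the comparison is between "patients diagnosed with HG and healthy pregnant women". No group sizes or ratio are given, and the section says that "a power analysis is not feasible".

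**The concern.** An assumption check with no stated consequence leaves two routes to a p-value.

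1. **Literal:** Student's t-test is used even when Levene's test rejects.
2. **Levene-selected:** the analyst reads the equal-variance or the unequal-variance row of the SPSS output, depending on Levene's result.

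Student's t pools the two variances. If sizes and SDs both differ, the pooled standard error is wrong. P-values are too small when the smaller group is the more variable, and too large when the larger group is. The second route reduces the distortion but does not remove it, because Levene's test often misses moderate inequality at these sizes, and the row is then chosen from the data. Equal groups would largely protect the test, but this is an observational cohort and nothing in the plan makes the groups equal.

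Every continuous variable that reaches the t-test is exposed. The documents do not show whether CCK or gallbladder volume will be among them.

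**Working it through.** The plan gives no sample size, SD or effect, so it has no figure to reproduce. From the plan come the 0.05 level, the named tests and SPSS. Group sizes, SD ratios, normal data and two-sided testing are assumptions.

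**Why Student's t drifts.** The true variance of the mean difference is s1²/n1 + s2²/n2. Student's t estimates, on average, [((n1−1)s1² + (n2−1)s2²)/(n1+n2−2)] × (1/n1 + 1/n2). With SDs of 2 and 1:

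- n = 20 (SD 2) v 40 (SD 1): true 4/20 + 1/40 = 0.225. Pooled (19×4 + 39×1)/58 × 0.075 = 0.149. The true variance is 1.51 times the pooled one, so the test is too liberal.
- n = 40 (SD 2) v 20 (SD 1): true 4/40 + 1/20 = 0.150. Pooled (39×4 + 19×1)/58 × 0.075 = 0.226. The ratio is 0.66, so the test is too conservative.
- n = 30 v 30: true 4/30 + 1/30 = 0.167. Pooled 2.5 × 2/30 = 0.167. The ratio is 1.00.

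**Type I error by simulation.** Equal means, 100,000 replicates per row, Levene centred on the mean and tested at 0.05:

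| n (more variable group first) | SD ratio | Student | Levene-selected | Welch | Levene rejects |
|---|---|---|---|---|---|
| 20 v 40 | 1.25 | 6.8% | 6.2% | 5.0% | 19% |
| 20 v 40 | 1.5 | 8.7% | 6.5% | 5.1% | 48% |
| 20 v 40 | 2 | 11.2% | 5.7% | 5.1% | 89% |
| 40 v 20 | 1.25 | 3.5% | 4.1% | 5.0% | 17% |
| 40 v 20 | 1.5 | 2.6% | 4.0% | 4.9% | 43% |
| 40 v 20 | 2 | 1.7% | 4.7% | 5.0% | 87% |
| 30 v 40 | 1.25 | 5.8% | 5.4% | 5.0% | 22% |
| 30 v 40 | 1.5 | 6.3% | 5.4% | 4.9% | 58% |
| 30 v 40 | 2 | 7.4% | 5.1% | 5.0% | 95% |
| 40 v 30 | 1.25 | 4.2% | 4.4% | 4.8% | 21% |
| 40 v 30 | 1.5 | 3.9% | 4.7% | 5.0% | 55% |
| 40 v 30 | 2 | 3.4% | 5.0% | 5.1% | 95% |
| 30 v 30 | 2 | 5.3% | 5.1% | 5.1% | – |

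A second simulation with 20,000 replicates per case (standard error about 0.15 points) agreed on the cases in common. It also covered 3:1 groups. At 15 v 45 with the smaller group more variable and an SD ratio of 1.5, Student gave 10.9%, Levene-selected 7.8% and Welch 5.4%.

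**With the normality step included.** Here Shapiro-Wilk is applied in each group and Mann-Whitney is used if either fails. About 10% of truly normal datasets are diverted (40,000 replicates):

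| n (more variable group first) | SD ratio | Student | Levene-selected | Welch |
|---|---|---|---|---|
| 20 v 40 | 1.5 | 8.6% | 6.8% | 5.5% |
| 20 v 40 | 2 | 11.1% | 6.0% | 5.5% |
| 40 v 20 | 1.5 | 3.0% | 4.3% | 5.2% |
| 40 v 20 | 2 | 2.2% | 4.8% | 5.1% |
| 30 v 40 | 1.5 | 6.4% | 5.6% | 5.2% |
| 30 v 40 | 2 | 8.0% | 5.8% | 5.7% |
| 40 v 30 | 1.5 | 4.1% | 4.7% | 5.0% |
| 40 v 30 | 2 | 3.6% | 5.1% | 5.2% |

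Welch now runs from 5.0% to 5.7%. It is nearer 5% than Student in all eight rows, and nearer than the Levene-selected rule in seven. The exception, 40 v 30 at ratio 2, differs by 0.1 points.

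**The case against.** The strongest objection is that the harm is hypothetical. The documents point no more to 2:1 groups with a twofold SD ratio than to equal groups, and with equal groups Student's t is close to nominal. That is right, and it limits the severity. But the plan does not commit to equal groups, so it cannot rely on that protection.

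Second, the natural reading of a plan that names SPSS and Levene's test is that Levene chooses the output row. The distortion is then modest: at 30 v 40, 5.1% to 5.4% or 4.4% to 5.0%; at 20 v 40, at worst 6.5% or 4.0%. This also stands. The larger Student figures belong to the literal reading. Still, the switch is not written down, and it remains less reliable than using Welch throughout.

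Third, the remedy is partial. The choice between t-test and Mann-Whitney by Shapiro-Wilk is equally data-driven and stays in place. Under the full procedure at 30 v 40 and 40 v 30, Welch and the Levene-selected rule differ by only 0.1 to 0.4 points. Variables judged skewed gain nothing, and those may include the main measures. All of this is correct. It narrows the benefit, but gives no reason to prefer Student's t or an unwritten switch.

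**Conclusion.** The concern holds. Levene's test has no stated consequence, Student's is the only t-test named, and no design feature protects a pooled-variance test.

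The size depends on inputs that the plan does not supply. Over the SD ratios tried, from 1.25 to 2, literal use of Student's t gives 5.8% to 11.2% or 1.7% to 4.2% at 20 v 40 and 30 v 40, depending on which group is more variable. The extremes of about 11% and 2% need both 2:1 groups and a twofold SD ratio. Selection by Levene stays between 4.0% and 6.5% in the same cases, and Welch between 4.8% and 5.1%, before the normality step is added.

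This is a change that should be made because it is cheap and closes an open choice. It does not threaten the study, and it would make almost no difference if the groups turn out equal in size or if the key variables all go to Mann-Whitney.

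**What to change.** Replace the Student's t-test wording with: *Variables judged normal will be compared between the two groups with Welch's t-test (SPSS row: equal variances not assumed), whatever Levene's test shows.* Levene's result may be reported descriptively but should not choose the test.

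The work is one phrase in the SAP, and SPSS already prints the row. The statistical cost is some power when variances are in fact equal. Starting from 80% with Student's t, the loss is about 0.1 points or less at 20 v 20, 30 v 30 and 30 v 40. It is 0.8 at 20 v 40, 1.0 at 15 v 30, about 1.5 at 20 v 60, 1.8 at 10 v 20 and 3.3 at 10 v 30. The loss matters only if the groups are both very small and very unequal. The Shapiro-Wilk choice between the t-test and Mann-Whitney is a separate matter that this change does not settle.
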